Diacon Hospital, Bangalore:

[name], MD, DM – Lead Site Investigator and Lead Site Diabetologist

[name], MBBS, DPM – Lead Site Psychiatrist

* Co-Principal Investigators

Study Title:

INtegrating DEPrEssioN and Diabetes treatment (INDEPENDENT) Study

Coordinating Centre:

Madras Diabetes Research Foundation, Chennai, India

[name] – Lead Study Coordinator

Supported by:

National Institute of Mental Health (NIMH), National Institutes of Health, USA

Award # R01MH100390-01

Registration:

ClinicalTrials.gov NCT02022111

1 Study Objective

The objective of this study is to evaluate the sustained effectiveness of an integrated depression and diabetes care intervention (health worker-led participant-activation and decision-supported team reviews) compared to enhanced usual care (notifying the participant's usual provider of depressive symptoms) for diabetic participants in India who have clinically-significant depressive symptoms (Patient Health Questionnaire [PHQ-9] ≥ 10) AND one or more poorly-controlled CVD risk factor (HbA1c $\geq 8.0\%$, SBP ≥ 140 mmHg, or LDL-c ≥ 130 mg/dl) in a randomized controlled implementation trial of 400 participants at four clinic research sites over 36 months (12-month active intervention with 24-month extended phase to evaluate sustainability).

1.1 Primary Outcome

The sustained (24 month) difference in the proportion of trial participants in each arm achieving combined improvements in depressive symptoms and CVD risk factors ($\geq 50\%$ reduction in the Symptoms Checklist-20 items [SCL-20] score AND one or more of the following: $\geq 0.5\%$ reduction in HbA1c, ≥ 5 mmHg reduction in SBP, or ≥ 10 mg/dl reduction in LDL-c).

1.1.1 Hypothesis

Compared to the control group, a higher proportion of intervention participants (30% vs. 15%) will achieve combined improvements in depressive symptoms and CVD risk factor levels ($\geq 50\%$ reduction in SCL-20 score AND one or more of the following: $\geq 0.5\%$ reduction in HbA1c, ≥ 5 mmHg reduction in SBP, or ≥ 10 mg/dl reduction in LDL-c) at 24 months.

1.2 Secondary Outcomes

To evaluate global, individual, and economic effects of our multi-condition strategy, we will report a number of secondary outcomes *for each study arm at 12, 24 and 36 months*:

- 1) measures of "common effect," i.e., whether the intervention had a similar beneficial effect on all four main targets (SCL-20, HbA1c, SBP, LDL-c);¹
- 2) proportion of participants achieving all 3 CVD risk factor targets in the two groups;
- 3) mean reductions in four main targets (SCL-20 score; HbA1c; SBP; LDL-c);
- 4) proportion of participants achieving treatment targets or significant reductions in individual outcomes (reduced depressive symptoms [$\geq 50\%$ reduction in SCL-20], glycemic control [HbA1c $\leq 7.0\%$ or $\geq 0.5\%$ reduction], BP control [SBP ≤ 130 mmHg or ≥ 5 mmHg reduction], lipid control [LDL ≤ 100 mg/dl or ≥ 10 mg/dl reduction]);
- 5) mean utility, quality of life, and participant treatment satisfaction scores; and
- 6) mean health expenditures and within-trial cost-utility.

2 Background

2.1 Burdens of Mental and Cardio-metabolic Illnesses Globally and in India

Mental health conditions (depression, psychoses, substance abuse) are associated with huge morbidity, social, and economic burdens;² and depression is the leading cause of disability worldwide.² Diabetes accounted for 4.6 million deaths in 2011³ and CVD caused a third of global mortality.²

Mental health and cardio-metabolic illnesses (e.g., diabetes) also interact and there are several large meta-analyses showing bi-directional relationships between them.² For example, depression is a risk factor for development of type 2 diabetes,^{4,5} adversely affects self-care for diabetes,^{4,6} and worsens glycemic control⁷ and quality of life;² and diabetes is associated with increased risk of developing depression.⁸ In addition, risks of debilitating complications and mortality are all compounded when cardio-metabolic and mental illnesses co-exist or are poorly controlled.²

Depression affects 12.1% to 15.1% of adults² and diabetes affects over 65 million people in India.² Prevalence of depression is higher among those with pre-existing CVD risks (e.g., 19.7% of people with diabetes)² or CVD complications (e.g., neuropathy).^{9,10} Therefore, the absolute number of those affected by both conditions is sizeable and constitutes a group at elevated risk and in whom intervention may have considerable synergistic benefits.² In particular, better organized, more effective, and more responsive care delivery may reduce morbidity and mortality.²

2.2 Gaps in Implementation

For most cardio-metabolic diseases, current evidence-based guidelines recommend comprehensive medical management (i.e., treating all CVD risk factors together)² combined with lifestyle modifications (regular physical activity, healthier diet, tobacco avoidance and cessation).² Mental health conditions such as depression also require long-term, participant-empowered, and self-guided care¹¹ in collaboration with providers.¹² However, this type of comprehensive care is limited by prohibitive costs, weak health care systems, poor coordination, and shortage of skilled personnel, especially in low-and-middle-income countries. In India, where depression, diabetes, and CVD remain under-diagnosed and sub-optimally treated as individual conditions and in combination,² ≥60% of people with diabetes are not routinely achieving risk factor control targets and care for people with mental health disorders has been described as generally suboptimal,² with anti-depressants used by only half of all eligible subjects.

2.3 Rationale for Integrated Care

Both mental health and cardio-metabolic diseases are chronic, complex, progressive, and costly to care for.² Identification is a key initiating step towards clinical- and self-care for these conditions, and in both behavioral activation and motivation are critical for adherence to management plans. In addition, care is hampered by major barriers at the patient (e.g., stigma, motivation),² provider (e.g., clinical inertia to intensify treatment), and system (e.g., organization of care) levels, all of which interact with each other.

Given the similarities in course of disease and barriers to care, as well as the adverse interactions between these groups of conditions, integrated care that combines mental health management with cardio-metabolic risk reduction may provide efficient opportunities to reduce morbidity and improve physical and social functioning among patients experiencing these conditions together.² This is particularly important as an opportunity to identify previously-unrecognized depressive symptoms among people with diabetes as they may be contributing to poor control and fueling a vicious cycle. There are data to indicate that optimizing therapy for depression, HbA1c, SBP, and LDL-c together is associated with better outcomes than focusing on any one condition alone.² As an example of how this works in practice, exercise, weight loss, and better glycemic control — which are routinely employed for diabetes care — also lower depressive symptom burdens in people affected by both diabetes and depression.²

The gaps in implementation of evidence-based recommendations may be due to low awareness of one's conditions or what to do about them or low motivation at the patient-level, while at care provider and systems levels, lack of decision-support tools limit implementation of evidence-based guidelines (e.g., intensification plus follow-up of treatment regimens). The evidence suggests that targeting different levels

of barriers to care at the same time (e.g., patient motivation and provider inertia) using patient-centered care models² can enhance health outcomes and satisfaction for people with diabetes and depression.²

2.4 Experiences in Integrated Care and Preliminary Data

Drs. [name] and [name] are pioneers in structuring care for multiple conditions (stepped-care interventions led by trained nurses). They have developed a chronic disease-focused depression treatment model² that:

- targets symptoms of depression, motivation, and hopelessness with medication and behavioral therapy;
- targets CVD risk factor control by optimizing medication intensification and helping patients self-manage their conditions better (empowerment, coping mechanisms, and overcoming perceived barriers to self-care); and
- helps patients adopt positive self-management behaviors (e.g., smoking cessation, medication adherence).

This model of care has been associated with a significantly enhanced response to depression treatment as well as enhanced medical control of diabetes (better adherence; reductions in depressive symptoms; more depression-free days;² intervention costs offset by savings for medical care;² and sustained incremental improvements in HbA1c (-0.58%), SBP (-5.1mmHg), and LDL-c (-6.9mg/dl) compared to usual care controls).² Importantly, these findings have stimulated adoption of collaborative care models by health payers and managed care providers in the United States (US), advocacy by major health agencies, and similar research in other countries.² This integrated care model emphasizes how combined depression and medical therapies can increase each other's benefits.

The INDEPENDENT study leverages previous work in this area, merging and adapting models of integrated care delivery from the US (TEAMCare)² and India (CARRS Translation Trial)¹³ to improve psychosocial and metabolic outcomes, respectively, among participants in India who have diabetes and poorly controlled CVD risks and are also suffering from depressive symptoms. The study builds on existing Indo-US collaborations and a robust platform of information technology (experiences of developing decision-support software), skilled teams, trial logistics expertise, and local expertise.

2.5 The INDEPENDENT Study

This study will develop and test an integrated depression and diabetes care model in four ambulatory diabetes clinics in India. Our evaluation plan will generate usable evidence regarding effectiveness, quality of life, and costs.²

The collaborative care intervention in this study will incorporate unique aspects of Indian culture gathered from focus group discussions and in-depth interviews with participants, family members, and health care providers at all clinic research sites. We will endeavor to make the intervention more participant-centered, develop locally-understandable educational materials for participants in India, and identify ways to overcome stigma of mental health disorders while facilitating trustful therapeutic relationships between nurse managers and the participants and their families.

Several additional benefits will emerge from this study, including: (a) identifying unrecognized depressive symptoms among several hundred diabetic patients and working with their regular providers to manage this appropriately; (b) training a cadre of care coordinators (CC) who can motivate better self-care for high-risk individuals; (c) offering a toolbox of therapeutic options (family-centered or other culturally-sensitive activation models such as spirituality, yoga, or meditation) in order to customize care according to the individual's preferences; and (d) developing software technology that prioritizes participants for review,

prompts treatment plan recommendations and modifications, and makes case review meetings efficient by providing an overview of key participant indicators in one place (the “dashboard”).

3 Study Design

The study is a four site, single-blind, individually randomized controlled implementation trial. Blinding outcome assessments and randomization will limit biases and evenly distribute participant characteristics.

3.1 Study Timeline

INDEPENDENT Study						
Activities	Year 1	Year 2	Year 3	Year 4	Year 5	Year 6
Design and Planning						
Refining intervention components						
Recruitment of care coordinators and training						
Installation of decision-support software and on-site training						
Data Collection						
Participant screening, recruitment, enrollment, randomization						
12-month intervention and 24-month follow-up of participants (Total participation = 36-months)						
Analysis						
Data analysis and reporting of outcomes						

4 Selection and Enrollment of Participants

4.1 Sample Size

The study is powered on between-arm differences in the proportion achieving the primary outcome [*combined depression and CVD risk factor improvements* ($\geq 50\%$ reduction in SCL-20 **and** ≥ 1 of: $\geq 0.5\%$ reduction in HbA1c **or** $\geq 5\text{mmHg}$ reduction in SBP **or** $\geq 10\text{mg/dl}$ reduction in LDL-c)] at 24 months post-randomization. The sample size estimation is guided by: (1) studies in India^{14,15} and elsewhere^{16,17} showing that $<50\%$ of all people with diagnosed diabetes routinely achieve single or multiple CVD risk factor targets; and (2) published results by Katon¹⁸ demonstrating a 30% between-group absolute difference [60% (TEAMCare) vs. 30% (usual care)] in proportions of subjects achieving $\geq 50\%$ reduction in SCL-20 score at 12 months and 15% absolute difference [37% vs. 22%] in the proportion of subjects achieving significant reductions or target control for all three CVD risk factors [HbA1c, SBP, LDL-c]. It is anticipated that a 15% absolute difference [30% of intervention arm participants will achieve combined and sustained reductions in depressive symptoms **plus** ≥ 1 CVD risk factor at 24-months post-randomization, compared to 15% of usual care participants]. Using a two-sample test of equality of proportions and a normal approximation with a continuity correction in Stata Version 12.0., we calculated that $n=268$ provides 80% power, and $n=335$ allows additional 20% for loss to follow-up. The aim is to recruit an enhanced sample of 360 participants, assigned equally to the two arms with the goal of randomizing 120 participants across the four clinic sites.

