4.2 Participant Screening

The population for this study will be Asian Indian, clinic-attending diabetes participants 35 years of age or older, with depressive symptoms (a PHQ-9 score ≥ 10) and at least one poorly controlled CVD risk factor (HbA1c $\geq 8.0\%$, SBP ≥ 140 mmHg, or LDL-c ≥ 130 mg/dl).

Project coordinators at each diabetes clinic research site will review existing electronic records or paper charts to identify participants with diabetes and one or more poorly controlled CVD risk factor (HbA1c $\geq 8.0\%$, SBP ≥ 140 mmHg, or LDL-c ≥ 130 mg/dl) in the previous six months. The coordinator will contact these participants and invite them to visit the clinic or complete the initial screening assessment by phone. During this interaction, participants will provide verbal consent, and respond to the nine-item PHQ-9 depression scale (see Appendix A) as a screener for depressive symptoms and additional questions to identify presence of other exclusion criteria (recent cardiovascular events or life-threatening cancer or kidney disease). Based on the prevalence of depression among people with diabetes and previous studies,² we anticipate screening 7,500 participants to recruit and randomize 400 participants.

The PHQ-9 helps ascertain presence of depression symptoms and functional impairments, and provides a gauge of depression severity (0-3 scoring for each item). The PHQ-9 is based on criteria for major depressive disorder in the Diagnostic and Statistical Manual Fourth Edition (DSM-IV) and has high sensitivity and specificity for depression symptoms.² This scale is an open source tool, has been translated into multiple languages,¹⁹ and has been used extensively and successfully in our past US and India studies.² PHQ-9 scores ≥ 10 have been shown to be associated with chronicity of depression⁴⁶ and predictive of adverse outcomes (dementia, mortality).² Individuals with scores of 10-12 benefit from intervention as much as those with scores of 14-15.²

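### The recruitment target is 360 in section 4.1 but 400 in sections 1 and 4.2, and section 4.1 adds a figure of 120 that fits neither

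*Combined protocol and SAP*

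**What the plan says.** Section 4.1 sizes the trial on the 24-month primary outcome, 30% against 15%, and reports that "we calculated that $n=268$ provides 80% power, and $n=335$ allows additional 20% for loss to follow-up". It then moves to a larger target and adds a second figure in the same sentence: "The aim is to recruit an enhanced sample of 360 participants, assigned equally to the two arms with the goal of randomizing 120 participants across" (its last words name the four sites).

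Two other sections give a different total. Section 1 describes the study as being conducted "in a randomized controlled implementation trial of 400 participants at four clinic research sites over 36 months". In section 4.2 the screening plan reads "we anticipate screening 7,500 participants to recruit and randomize 400 participants". Section 3 confirms the number of sites: "The study is a four site, single-blind, individually randomized controlled implementation trial".

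**The concern.** Three different numbers are offered for how many people are to be randomised, and all of them stand in the current body text. Someone working from section 4.1 would close recruitment 40 participants earlier than someone working from section 1 or 4.2. A stop at 360 would be full accrual under one section and a 10% shortfall (40/400) under the other two.

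Oversight depends on this number as well. Section 9 has the Coordinating Center monitor enrolment and allows early discontinuation to be considered if completion becomes less likely. Section 9.1 has the DSMB monitor recruitment. Neither can judge progress consistently without one agreed target. The choice also sets how much loss over 24 months the primary analysis can absorb.

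**Working it through.** **Inputs.** Event rates 0.15 and 0.30 (sections 1.1.1 and 4.1). Two-sample test of proportions, normal approximation with continuity correction, 80% power, 20% loss and equal allocation (section 4.1). Four sites (section 3). The significance level is not stated. Two-sided 0.05 is assumed because it reproduces the plan's figure; one-sided 0.05 with the correction gives 216 in total, which does not.

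**Reproducing 268 and 335.** With d = 0.15 and mean rate 0.225:

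- Uncorrected n per arm = [1.960 × √(2 × 0.225 × 0.775) + 0.842 × √(0.15 × 0.85 + 0.30 × 0.70)]² / 0.15² = 120.47.
- Corrected n per arm = (120.47/4) × [1 + √(1 + 4/(120.47 × 0.15))]² = 133.47, rounded up to 134.
- Total = 2 × 134 = 268. After 20% loss: 268/0.8 = 335.

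Both figures agree with section 4.1. Neither 360 nor 400 comes out of this calculation; each is a round number above 335.

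**Comparing the two totals.** Power is found by inverting the continuity correction at the evaluable number per arm.

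| | 360 | 400 |
|---|---|---|
| Margin over 335 | 25 | 65 |
| Evaluable after 20% loss | 288 (144 per arm) | 320 (160 per arm) |
| Continuity-corrected power after 20% loss | 83.2% | 87.2% |
| Loss tolerated before falling below 268 | 1 − 268/360 = 25.6% | 1 − 268/400 = 33.0% |
| Average per site (four sites) | 90 | 100 |

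For reference, the same method gives 80.2% at 335 randomised (268 evaluable).

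**Can 360 and 400 be different quantities?**

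- Not recruited against evaluable. The 360 are to be divided between the arms, and the 400 are to be randomised, so both count randomised participants.
- Not 360 plus an allowance for loss. That allowance was already made in going from 268 to 335.

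**Can 120 be made to fit?**

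- As a total, it is below 268.
- Per arm, 120 × 2 = 240, also below 268.
- Per site, 120 × 4 = 480, which matches neither total.
- 120 × 3 = 360, but that needs three sites and section 3 has four. Whether the figure is left over from a three-site design cannot be settled from the document.

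**Screening.** 7,500/400 = 18.75 screened per participant randomised. At the same ratio, 360 would need 18.75 × 360 = 6,750.

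**The case against.** The strongest reply is that nothing of statistical substance changes. The calculation is correct, either total exceeds 335, and the test, allocation and type I error are unaffected. Section 4.1 is the section that sets the size, and it states an explicit aim of 360. The 400 in section 4.2 is an expectation within a screening estimate. No passage sets out a formal rule for closing recruitment, so confusion over when to stop is a possibility, not something the text makes certain. The 120 could be a plain slip.

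Most of this is fair, and it limits the weight of the point. It does not remove the conflict. Section 1 states 400 as the size of the trial without qualification, and no section is given precedence. The lack of a closing rule makes the total more important, since it is the only indication of when accrual is complete. Two suggestions are optional. Reporting power at the chosen total is good practice, not the repair of an error. Keeping 7,500 screened with 360 randomised would only imply a yield of 4.8% instead of 5.3%.

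**Conclusion.** The inconsistency is real: the plan does not give a unique recruitment target. The gap is 40 participants, or about 83% against 87% power after the planned 20% loss, and 25.6% against 33.0% loss tolerated. The power figures assume two-sided 5%, the 15% and 30% rates, and equal arms. No loss of the stated 80% power is shown under either total. The 120 is wrong as written, because it matches neither total on any four-site reading. The point should be corrected, but it does not call the design into question.

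**What to change.** - State one total in sections 1, 4.1 and 4.2. The choice between 360 and 400 is the sponsor's; either meets the design power.
- Delete or correct the 120. If a site figure is wanted, give it as an average (90 for 360, 100 for 400) and say that no equal quota is implied.
- Beside the 80% at 268 evaluable, add the continuity-corrected power after 20% loss at the chosen total (about 83% or 87%), together with the significance level it uses.
- If 360 is chosen, consider rescaling the screening figure in section 4.2 to about 6,750. If 400 is chosen, 7,500 stands.

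The cost is wording in up to three sections, with no change to the sample size calculation, the test or the allocation.

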4.2 Participant Screening

The population for this study will be Asian Indian, clinic-attending diabetes participants 35 years of age or older, with depressive symptoms (a PHQ-9 score ≥ 10) and at least one poorly controlled CVD risk factor (HbA1c $\geq 8.0\%$, SBP ≥ 140 mmHg, or LDL-c ≥ 130 mg/dl).

Project coordinators at each diabetes clinic research site will review existing electronic records or paper charts to identify participants with diabetes and one or more poorly controlled CVD risk factor (HbA1c $\geq 8.0\%$, SBP ≥ 140 mmHg, or LDL-c ≥ 130 mg/dl) in the previous six months. The coordinator will contact these participants and invite them to visit the clinic or complete the initial screening assessment by phone. During this interaction, participants will provide verbal consent, and respond to the nine-item PHQ-9 depression scale (see Appendix A) as a screener for depressive symptoms and additional questions to identify presence of other exclusion criteria (recent cardiovascular events or life-threatening cancer or kidney disease). Based on the prevalence of depression among people with diabetes and previous studies,² we anticipate screening 7,500 participants to recruit and randomize 400 participants.

The PHQ-9 helps ascertain presence of depression symptoms and functional impairments, and provides a gauge of depression severity (0-3 scoring for each item). The PHQ-9 is based on criteria for major depressive disorder in the Diagnostic and Statistical Manual Fourth Edition (DSM-IV) and has high sensitivity and specificity for depression symptoms.² This scale is an open source tool, has been translated into multiple languages,¹⁹ and has been used extensively and successfully in our past US and India studies.² PHQ-9 scores ≥ 10 have been shown to be associated with chronicity of depression⁴⁶ and predictive of adverse outcomes (dementia, mortality).² Individuals with scores of 10-12 benefit from intervention as much as those with scores of 14-15.²

